1. STUDY DETAILS

1.1 Study objectives

Following are the study primary and secondary objectives (per protocol amendment v3.0).

Primary Objectives

| Objective | Endpoint |
|--|--|
| 1. To assess the safety and tolerability of 2 dosing regimens of benralizumab for adult patients during the 56-week treatment period and through the follow-up period (16 weeks from day of last dose). 2. To assess the safety and tolerability of 2 dosing regimens of benralizumab for adolescent patients during the 108-week treatment period and through the follow-up period (16 weeks from day of last dose). | 
 • AEs/SAEs • Laboratory variables • Physical examination |

Secondary Objectives

| Objective | Endpoint |
|--|---|
| 1. To evaluate the effect of 2 dosing regimens of benralizumab on asthma exacerbations in adult patients during the 56-week treatment period and through the follow-up period (16 weeks from day of last dose). 2. To evaluate the effect of 2 dosing regimens of benralizumab on asthma exacerbations in adolescent patients during the 108-week treatment period and through the follow-up period (16 weeks from day of last dose). | 
 • Annual asthma exacerbation rate, where an asthma exacerbation is defined by a worsening of asthma requiring the use of systemic corticosteroids for at least 3 days, and/or an in-patient hospitalisation, and/or an emergency department or urgent care visit. |

Secondary Objectives

| Objective | Endpoint |
|--|--|
| 
 1. To evaluate the effect of 2 dosing regimens of benralizumab on health care utilisation and work and productivity loss for adult patients during the 56-week treatment period and through the follow-up period (16 weeks from day of last dose) 2. To evaluate the effect of 2 dosing regimens of benralizumab on health care utilisation and work and productivity loss for adolescent patients during the 108-week treatment period and through the follow-up period (16 weeks from day of last dose) | 
 • WPAI+CIQ • Hospitalisations, emergency department (ED) visits, urgent care visits and all other outpatient visits due to asthma |
| 
 1. To assess the effect of 2 dosing regimens of benralizumab on asthma related and general health-related quality of life for adult patients during the 56-week treatment period and through the follow-up period (16 weeks from day of last dose) 2. To assess the effect of 2 dosing regimens of benralizumab on asthma related and general health-related quality of life for adolescent patients during the 108-week treatment period and through the follow-up period (16 weeks from day of last dose) | 
 • AQLQ(S)+12 • EQ-5D-5L |
| 
 1. To assess the effect 2 dosing regimens of benralizumab on asthma control for adult patients during the 56-week treatment period and through the follow-up period (16 weeks from day of last dose) 2. To assess the effect 2 dosing regimens of benralizumab on asthma control for adolescent patients during the 108-week treatment period and through the follow-up period (16 weeks from day of last dose) | 
 • ACQ-6 |

| Objective | Endpoint |
|--|--|
| 
 1. To evaluate the pharmacokinetics and immunogenicity of 2 dosing regimens of benralizumab for adult patients during the 56-week treatment period and through the follow-up period (16 weeks from day of last dose) 2. To evaluate the pharmacokinetics and immunogenicity of 2 dosing regimens of benralizumab for adolescent patients during the 108-week treatment period and through the follow-up period (16 weeks from day of last dose) | 
 • PK parameters • Anti-drug antibodies (ADA) |
| 
 1. To assess the effect of 2 dosing regimens of benralizumab on pulmonary function for adult patients during the 56-week treatment period (16 weeks from day of last dose) 2. To assess the effect of 2 dosing regimens of benralizumab on pulmonary function for adolescent patients during the 108-week treatment period (16 weeks from day of last dose) | 
 • Pre-bronchodilator FEV₁ and post-bronchodilator FEV₁ at the study centre |
| 
 1. To assess the impact of 2 dosing regimens of benralizumab on blood eosinophil levels for adult patients during the 56-week treatment period and through follow-up period (16 weeks from day of last dose) 2. To assess the impact of 2 dosing regimens of benralizumab on blood eosinophil levels for adolescent patients during the 108-week treatment period and through the follow-up period (16 weeks from day of last dose) | 
 • Blood eosinophils |

1.2 Study design

This is a double-blind, randomised, parallel group, extension study designed to evaluate the safety and tolerability of a fixed 30 mg dose of benralizumab administered subcutaneously (SC). Patients who complete 1 of the predecessor studies D3250C00017 (SIROCCO), D3250C00018 (CALIMA), or D3250C00020 (ZONDA) on investigational product (IP) may

be eligible to enrol into this study. Patients who enrol in the study will follow the flow charts as shown in [Figure 1](#), [Figure 2](#), and [Figure 3](#).

[figure not shown]
After a minimum of 1200 patients have been enrolled in this study, subsequent patients (up to a maximum of 2200 total for the study), who complete a minimum of 16 weeks, and no more than 40 weeks, in this study, will be given the option to transition to an open-label safety extension study, Study D3250C00037 (MELTEMI), which retains patients on the same treatment regimen as in BORA and contains a simplified set of study assessments.

Patients choosing to enter MELTEMI will complete an end-of-treatment (EOT) visit in BORA before transitioning. Adolescent patients, patients from Japan and South Korea, and any patient who chooses not to enter MELTEMI will remain in BORA through IP discontinuation (IPD) or EOT and follow-up (FU).

Once the blind is broken in the predecessor studies, BORA becomes a single-blind design for those patients who had been on active treatment in the predecessor studies. The study will become single-blind for all remaining patients at the time of the Japanese EOT analysis and when all country regulatory required approvals are received for the protocol amendment that details the reporting and unblinding plan. While the Sponsor will be unblinded to regimen for analysis purposes, study conduct and blinding at the site and patient level will remain unchanged.

Figure 1 Adults study flow charts

Adults previously assigned to an active treatment arm in the predecessor study

Adults previously assigned to the placebo arm in the predecessor study

[figure not shown]
[figure not shown]

Figure 2 Adolescent study flow charts (outside the EU)

Adolescents outside the EU previously assigned to an active treatment arm in the predecessor study

Adolescents outside the EU previously assigned to the placebo arm in the predecessor study

[figure not shown]
[figure not shown]
[figure not shown]

Figure 3 Adolescent study flow charts (within the EU)

Adolescents within the EU previously assigned to an active treatment arm in the predecessor study

Adolescents within the EU previously assigned to the placebo arm in the predecessor study

1.3 Number of subjects

Patients who complete the double-blind treatment period on IP in 1 of the predecessor studies, SIROCCO, CALIMA, or ZONDA, may be eligible to enrol into BORA. With an estimated rollover rate of >90% from these preceding studies, this safety extension study will enrol approximately 1800 to 2000 patients, up to a maximum of 2200 patients worldwide. The first 1200 adult patients will remain in BORA through IPD or EOT and FU. The remaining 700-1000 adult patients will be asked to transition into the safety extension study, MELTEMI. Adolescent patients and patients from Japan and South Korea will remain in BORA through IPD or EOT and FU.

A minimum of 1200 patients is considered sufficient to address the primary objective of safety and tolerability in the on-treatment and 16-week safety FU period of BORA. The safety extension study, MELTEMI, will allow remaining patients to continue to receive benralizumab until it is available in their local market or until it has been withdrawn from the approval process in their local market. The minimum 16-week treatment period prior to the transition to MELTEMI ensures that any patients previously randomised to placebo have

completed monthly study visits and assessments for the first 3 active doses within BORA before transitioning to MELTEMI.

The study is not designed to power the statistical testing of any null hypothesis.

2. ANALYSIS SETS

As a result of a GCP breach outlined below, all data from the BORA site Redacted in Redacted will be excluded from all analysis sets outlined below, tables and figures. Data from this site will still be included in data listings in BORA.

Following review of anomalous pharmacokinetic (PK) results from the predecessor studies, a for cause audit was conducted at SIROCCO centre Redacted (centre Redacted in BORA). The audit and responses provided by the principal investigator (PI) Redacted could not establish a root cause for the anomalous PK results. During the audit, the site staff redacted personal identification data in source documentation making it impossible to reconstruct the study data entered into the database in order to assess the validity of the data reported.

AstraZeneca decided to close the BORA trial at this site and considered this a GCP breach and a report of a potential scientific misconduct was submitted by AstraZeneca to the FDA on 22 November 2016. All 10 subjects at the site withdrew informed consent to be contacted further.

2.1 Definition of analysis sets

In the analysis sets outlined below, data from patients who do not enrol into MELTEMI are the primary data source and are summarised separately from patients who enrol into MELTEMI unless otherwise noted in the following sections. Patients must have provided their informed consent. If no signed informed consent is collected (major protocol deviation), then the patient will be excluded from all analysis sets defined below.

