3.7 Withdrawal from the study

3.7.1 Withdrawal of Informed Consent

Patients are free to withdraw from the study at any time (IP and assessments) without prejudice to further treatment. Patients who discontinue IP will be discontinued from the study.

A patient who withdraws consent will always be asked about the reason(s) and the presence of any adverse events (AE). The Investigator will follow up AEs outside of the clinical study. The enrolment/randomization code of the withdrawn patient cannot be reused.

If patient agrees, he/she will be asked to return to the study center and complete procedures described for the IPD and FU visits within 4 weeks (+7 days) and 16 weeks (\pm 7 days) after the last dose of IP, respectively.

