4.2.2 Patients that will transition into MELTEMI

Patients who enter BORA after approximately 1200 adults have enrolled will be asked to transition into the separate safety extension study, MELTEMI, after completing a minimum of

16 weeks and a maximum of 40 weeks in BORA (ie, patients may transition at Visit 5, 7, 9, or 11).

Patients must transition from BORA into MELTEMI at the earliest possible odd-numbered BORA visit following all necessary approvals being in place at the study site, AND after database lock of the trial in which the patient entered this program (the latter will be confirmed to sites once this milestone is reached). Patients may transition into MELTEMI only at Visits 5, 7, 9, or 11 of this study.

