4. ANALYSIS METHODS

4.1 General principles

The age group classification for adult and adolescent from the predecessor studies will be used in the BORA subgroup analysis. If the patient's age at the time of enrolment in the previous study was between 12 and 17 years old then he/she was considered as part of the adolescent group even if the patient was 18 years old at the time of entry in to BORA study. If it was between 18 and 75 years old, he/she was considered as part of adult group. Actual age calculated at BORA study entry will be used in descriptive summary of age and listings.

Patients randomised to placebo in the predecessor study will be summarised separately from patients randomised to benralizumab. The presentation of treatment group will combine treatment assigned in both BORA and the predecessor study as follows:

- Benra 30 mg q.4 weeks
 - Predecessor q.4 weeks
 - Predecessor placebo
- Benra 30 mg q.8 weeks

- Predecessor q.8 weeks
- Predecessor placebo

The analysis of the primary and secondary endpoints will include all data captured during the study, unless the patient withdraws consent, and assent, where applicable, regardless of whether study treatment was prematurely discontinued or delayed, and/or irrespective of protocol adherence. Any data collected after a patient is transitioned into the long-term extension study MELTEMI will not be included in the analyses described in this SAP.

Summary data will be presented in tabular format by treatment. Categorical data will be summarised by the number and percentage of patients in each category. Continuous variables for parametric data will be summarised by descriptive statistics including n, mean, standard deviation, median, minimum value and maximum value unless otherwise specified.

All endpoints as describe in previous sections will be summarised descriptively. The study is not a confirmatory study, thus in general no hypothesis testing and/or p-values will be provided. Following are sets of planned groups for the study.

The primary source of data for the clinical study report (CSR) summaries will be based on patients who stayed in the BORA study. The analyses will follow the two phases as described in the protocol amendment. Some selective summaries will be separately presented for the patients who enrolled into MELTEMI study.

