4.2.5.1 Adverse events

Adverse events (AEs) will be summarised separately by the treatment group for the on-study, on-treatment and post-treatment periods, as defined in Section 3.1.1.

An overall summary table will be produced showing the number and percentage of patients with at least 1 AE in any of the following categories; AEs, serious adverse events (SAEs), deaths due to AE, and AEs causing discontinuation of the investigational product (DAEs). This summary will also be repeated by baseline blood eosinophil count ($<300/\mu\text{L}$, $\geq 300/\mu\text{L}$) for the on-study and on-treatment periods. The total number of AEs in the different AE categories in terms of AE counts will also be presented (ie, accounting for multiple occurrences of the same event in a patient).

AEs will be summarised by System Organ Class (SOC) and Preferred Term (PT) assigned to the event by MedDRA. For each PT, the number and percentage of patients reporting at least one occurrence will be presented, ie, for a patient multiple occurrences of an AE will only be counted once.

A summary of the most common (frequency of $\geq 5\%$ in any treatment group) AEs will be presented by PT. AEs (by PT) will be summarised by causality and maximum intensity. If a patient reports multiple occurrences of the same AE, the maximum intensity will be taken as the highest recorded maximum intensity (the order being mild, moderate, and severe). SAEs, DAEs, and deaths will also be summarised in separate tables.

Furthermore, events of interests such as injection site adverse events, hypersensitivity adverse events, adjudicated MACE+, and malignancies will be summarised separately.

The rate of AEs per person-years at risk, calculated as (number of patients reporting AE)/(total period with patients at risk of AE), will be reported for the on-study, post-treatment and on-treatment periods. The total period at risk for each patient within each study period will follow the definitions specified in Sections 3.1.1. Rates will typically be expressed in terms of events per 100 patient-years.

Separate listings of patients with AEs, SAEs, death due to AE, discontinuations due to AEs, as well as events of interest will be presented.

For the patients who rolled over to MELTEMI study, selective AE and SAE tables during study period will be summarised by treatment group. A listing of adjudicated MACE+ and malignancies will be also provided.

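### The primary adult safety tables leave out patients who moved to MELTEMI, so on-treatment and on-study rates of death and of AEs stopping treatment exceed the rates in all dosed adults censored at transition

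*SAP*

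**What the plan says.** SAP 2.1 sets the population for the main tables: "data from patients who do not enrol into MELTEMI are the primary data source and are summarised separately from patients who enrol into MELTEMI", unless later sections say otherwise. SAP 4.1 repeats the rule for the CSR: "summaries will be based on patients who stayed in the BORA study". Protocol 8.3 and 8.5 also separate the two groups of adults.

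The selecting event comes after dosing. Under SAP 1.3 the first 1200 adults remain in BORA and a further 700-1000 are asked to move. Protocol 4.2.2 fixes the timing: "Patients may transition into MELTEMI only at Visits 5, 7, 9, or 11 of this study", that is Week 16, 24, 32 or 40. Site approvals must be in place, "AND after database lock of the trial in which the patient entered this program". Adolescents, patients in Japan and South Korea, and adults who decline all stay.

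Stopping treatment ends participation: "Patients who discontinue IP will be discontinued from the study" (Protocol 3.7.1). MELTEMI is described in SAP 1.2 as a study "which retains patients on the same treatment regimen as in BORA and contains a simplified set of study assessments".

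SAP 4.2.5.1 defines the AE rate per 100 patient-years as "calculated as (number of patients reporting AE)/(total period with patients at risk of AE"), for the on-study, on-treatment and post-treatment periods. For patients who moved to MELTEMI it plans only that "selective AE and SAE tables during study period will be summarised by treatment group", plus a listing of adjudicated events and malignancies. It plans no AE table for all dosed adults together. SAP 4.2.4 does tabulate exposure for the patients who moved.

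**The concern.** Whether a late-enrolled adult appears in the primary safety tables depends on what happens to that patient on treatment. A death before the transition visit keeps the patient in. A DAE does the same if patients who have stopped IP cannot enter MELTEMI. A patient who gets through 16 to 40 weeks without either event and then moves is taken out, along with all that event-free time.

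For these two outcomes the numerator keeps every late-cohort event while the denominator loses person-time. The separate MELTEMI tables have the opposite selection: they can show essentially no BORA death or DAE. Neither set gives the rate among all adults who were dosed.

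Safety is the primary objective, and deaths and DAEs are lines in the overall AE table. A reader would naturally take the primary adult figures as the rates on benralizumab, and might compare them with other studies.

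**Working it through.** The plan states no death or DAE rate and is not powered for any test, so there is no figure of its own to reproduce.

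**Identity.** Let E be the deaths or DAEs, PY_p the primary-set patient-years and PY_m the BORA patient-years of those who moved. If those who moved had no such event before transition, E is the same in both rates:

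(E/PY_p) / (E/(PY_p + PY_m)) = 1 + PY_m/PY_p.

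This exceeds 1 whenever anyone transitions, whatever the hazard shape.

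**Inputs.** From the documents: 1200 adults not asked to move; 700-1000 asked; 2133 enrolled in all (Protocol synopsis), so at most 2133 - 1200 = 933 late adults, fewer once adolescents are removed; transition at Weeks 16-40; treatment to Week 56. Assumed: proportion stopping IP, proportion declining, and mean transition week.

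**Base case (assumed).** 933 late adults, 10% stopping by Week 56 at a constant hazard, transition at Week 28, 20% declining. Time at risk runs to the stop date.

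- Hazard = -ln(0.90)/(56/52) = 0.0978 per year. Still on IP at Week 28: 0.9487.
- Willing to move: 933 × 0.8 = 746.4. Of these, 746.4 × 0.0513 = 38.3 stop first and 708.1 transition.
- PY_m = 708.1 × 28/52 = 381.3.
- First 1200 plus 186.6 decliners: 1386.6 × (0.10/0.0978 = 1.0221) = 1417.3 PY. The 38.3 early stoppers add 10.2 PY. PY_p = 1427.5.
- On-treatment factor = 1 + 381.3/1427.5 = 1.27.
- On-study, adding 12 weeks for each of the 1424.9 primary patients (328.8 PY): 1 + 381.3/1756.3 = 1.22.

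**Range.** With 700, 933 or 1000 late adults, 5-15% stopping, Weeks 16-40 and 0-50% declining, the on-treatment factor runs from 1.065 to 1.582. A separate calculation with 850 late adults, 70% uptake and Week 28 gave 1482 PY retained of 1783, a factor of 1.20. If 80% of late adults stay, the factor is 1.02-1.07; if 90% stay, 1.01-1.03.

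**Against the full 56-week rate.** This comparison does depend on timing. The base case was kept, with other stopping at 7.8 per 100 PY and the DAE hazard changed at Week 28:

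| DAE hazard per 100 PY, before / after Week 28 | Primary ÷ 56-week rate | Pooled censored ÷ 56-week rate |
|---|---|---|
| 2 / 2 | 1.27 | 1.00 |
| 1 / 3 | 1.13 | 0.89 |
| about 0 / 4 | about 1.00 | about 0.78 |
| 4 / about 0 | about 1.52 | about 1.20 |

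**Illustration (base case, constant hazard).** A 2.0% 56-week DAE risk is 2.0/1.0221 = 1.96 per 100 PY and would be reported as 1.96 × 1.267 = 2.48. A 0.5% death risk is 0.49 and would be reported as 0.62.

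**Percentages.** Treating every stop as the event, the base case has 177.0 events (138.7 + 38.3). The primary set shows 177.0/1424.9 = 12.4% for a true 56-week risk of 10%. Crude pooling shows 177.0/2133 = 8.3%, too low because those who moved were followed for only part of the period.

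**The case against.** The split is pre-specified in both documents, the study is descriptive, and each rate is correct for the set the SAP defines. Exposure of those who moved is tabulated, so if they have no deaths or DAEs a reader could add their person-time to the denominator. The absolute shift is small for rare events and overstates harm. All of this stands, and it limits the consequence. It does not remove the selection, and no planned output makes the correction or warns the reader.

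The size is also open. Because transition needs site approvals and the predecessor study's database lock, a late adult who has passed Visit 11 before then cannot move. Retention could then be well above 50% and the factor close to 1. The DAE part is an inference from Protocol 3.7.1 and SAP 1.2, since MELTEMI's entry rules are not in these documents; only for deaths is it certain.

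A reader might infer that the factor measures the excess over the true 56-week rate. It does so only under a constant hazard. A reader might also take the pooled censored rate as the right answer. It gives more weight to early person-time and can fall about 20% below the 56-week rate when events come late.

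**Conclusion.** The concern holds within limits. On-treatment and on-study adult death rates in the primary tables exceed the all-dosed rates censored at transition, and so do DAE rates if patients who have stopped IP cannot enter MELTEMI. That direction needs no hazard assumption.

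The size rests on assumed uptake, timing and stopping: about 1.065-1.58 on-treatment at 50-100% uptake, smaller on-study, and 1.01-1.07 if 80-90% of late adults stay. SAP 4.1.1 reports SIROCCO/CALIMA and ZONDA patients separately and transition waits for each study's lock, so the factor will differ between those tables. Relative to the 56-week rate the primary figure could be about right (late events), 1.27 times too high (base case, constant hazard) or about 1.5 times too high (early events).

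A reader might infer that all the safety results are biased, or that the comparison of regimens is. The documents do not support either. Patients who move have no post-treatment time in BORA, so post-treatment rates do not change. For AEs that do not end participation, laboratory variables and physical examination, those who move take their findings with them and the direction is not fixed. The rule applies to both regimens, so the Q4W/Q8W contrast is little affected. Disposition and adolescent-only tables are not affected. This is a worthwhile, inexpensive improvement to a descriptive plan.

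**What to change.** Add to SAP 4.2.5.1 one or both of the following, by treatment group:

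- Death, DAE and SAE percentages and rates per 100 patient-years for adults in a group fixed at entry: the first approximately 1200 adults plus those in Japan and South Korea, whom SAP 1.3 already plans to follow through EOT and follow-up.
- A cumulative incidence to Week 56 for all dosed adults, censored at the MELTEMI transition visit.

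Footnote the primary adult tables to say that membership depends on not entering MELTEMI and that death and DAE rates are affected. A pooled all-dosed rate censored at transition may be added if labelled as weighted toward early person-time. Crude pooled percentages should not be used.

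The cost is SAP wording and one extra table set, with no new data. Late-enrolled adults outside Japan and South Korea who decline MELTEMI would not appear in the entry-fixed table, though they do count in the all-dosed cumulative incidence.
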